1.1.2 Secondary Objectives

Immunogenicity:

- To assess the immune response of VLA15 in healthy adults aged 18 - 65 years up to Month 12 (i.e. 10 months after the primary vaccination series).

Safety:

- To assess the safety profile of VLA15 in healthy adults aged 18 - 65 years up to Month 12.

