2.12 Columns in Tables

All tables will be presented by treatment group, i.e. every treatment group will be shown in a separate column. Tables described at overall study information (Section 3), baseline evaluation (Section 4) and safety analysis (Section 6) will show one column per treatment group (i.e. 90 µg, 135 µg, 180 µg and Placebo) a column for the three VLA15 treatment groups pooled and a column for all subjects pooled. Tables defined in Section 5 will show one column for each treatment group. Statistical analyses will pool subjects from both Run-in and Main Study phase.

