6.1.3 Inferential Analysis for Adverse Events

95% confidence intervals according to Altman will generally be provided for all AE rates. Differences between the four treatment groups will be assessed for significance using Fisher's exact (Fisher-Freeman-Halton) test, whereby a significant overall test will be amended by pair-wise tests.

It is stated in detail in Section 7 for which tables such comparisons will be made.

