7.1.4 Safety

No	Legend	IA D85	IA D236	Content/Comment
Table 14.1.4.1:	Summary Table of Adverse Events (solicited and unsolicited) (Safety Population)	X	X	Including statistical test • Any AE, related AE, severe AE, related

				severe AE, SAE, related SAE, medically attended AE, related medically attended AE, AE leading to withdrawal from study, AE leading to withdrawal from further vaccination 
 • Any solicited AE, severe solicited AE, solicited local AE, severe solicited local AE, solicited systemic AE, severe solicited systemic AE • Any unsolicited AE, related unsolicited AE, severe solicited AE, related severe solicited AE, unsolicited SAE, medically attended unsolicited AE, unsolicited AE leading to withdrawal from study, unsolicited AE leading to withdrawal from further vaccination, AE of special interest, related AE of special interest
Table 14.1.4.2:	Summary Table of Adverse Events by Age group (solicited and unsolicited) (Safety Population)	X	X	Including statistical test Content see table 14.1.4.1
Table 14.1.4.3:	Summary Table of Adverse Events by Region (solicited and unsolicited) (Safety Population)	X	X	Including statistical test Content see table 14.1.4.1
Table 14.1.4.4:	Summary Table of Adverse Events by B.b. s.l. serostatus (solicited and unsolicited) (Safety Population)	X	X	Including statistical test Content see table 14.1.4.1
Table 14.1.4.5:	Summary Table of Adverse Events (solicited and unsolicited) by Vaccination Period (Safety Population)	X	X	Including statistical test Content see table 14.1.4.1
Table 14.1.4.6:	Subjects with Solicited and Unsolicited Serious	X	X	Including statistical test

	Adverse Events by SOC and PT (Safety Population)			
Table 14.1.4.7:	Subjects with Solicited and Unsolicited Related Serious Adverse Events by SOC and PT (Safety Population)	X	X	Including statistical test
Table 14.1.4.8:	Subjects with Solicited and Unsolicited Medically Attended Adverse Events by SOC and PT (Safety Population)	X	X	Including statistical test
Table 14.1.4.9:	Subjects with Solicited and Unsolicited Related Medically Attended Adverse Events by SOC and PT (Safety Population)	X	X	Including statistical test
Table 14.1.4.10:	Subjects with Solicited and Unsolicited Adverse Events Leading to Withdrawal from Further Vaccination by SOC and PT (Safety Population)	X	X	Including statistical test

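### Section 6.1.3 never sets pooled VLA15 against placebo, which costs about 6 to 14 points of power for adverse events that are not rare and occur at similar rates across doses

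*SAP*

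**What the plan says.** Section 1.1.2 states the safety objective for the vaccine as a whole: "To assess the safety profile of VLA15 in healthy adults aged 18 - 65 years up to Month 12". Section 2.12 gives the safety tables one column per treatment group plus "a column for the three VLA15 treatment groups pooled and a column for all subjects pooled", and pools the two study phases.

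The inference is fixed in Section 6.1.3: "Differences between the four treatment groups will be assessed for significance using Fisher's exact (Fisher-Freeman-Halton) test". Comparisons of two groups at a time depend on that result: "whereby a significant overall test will be amended by pair-wise tests". For estimation the same section says "95% confidence intervals according to Altman will generally be provided for all AE rates"; these are intervals for single rates. For detail it refers onward: "It is stated in detail in Section 7 for which tables such comparisons will be made". Section 7.1.4, however, only marks tables as including a test, from Table 14.1.4.1 ("Summary Table of Adverse Events (solicited and unsolicited) (Safety Population") onward. It names no contrast.

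**The concern.** The plan displays all vaccinated subjects together but never compares that column with placebo. An obvious question for unsolicited, related, severe or medically attended AEs is whether the vaccine raises the rate at all, and a similar increase at each dose is a reasonable alternative to plan for. Against that alternative a four-group test spends two of its three degrees of freedom on differences between doses. The follow-up tests use one dose group at a time and run only if the overall test succeeds. A real vaccine effect on a commoner AE can then be reported as no significant difference, although the totals printed in the same row would have shown it. Safety is a secondary objective, so no primary conclusion is at risk. What is lost is sensitivity to a safety signal in a trial meant to supply the safety database before Phase 3.

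**Working it through.** **The plan's own figures.** Section 1.4 gives no power for AE comparisons. Its one power figure, for Day 85 GMTs, reproduces: log10(86.1/61.3) = 0.1475, so n = 2 × (1.960 + 0.842)² × 0.51² / 0.1475² ≈ 188 per group, and 189 per group gives 80.3% (stated: 189 and 80%). The zero-event limits also reproduce: 1 − 0.05^(1/30) = 9.5% (stated below 10%) and 1 − 0.05^(1/210) = 1.42% (stated 1.4%).

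**Inputs.** From Section 1.2, with phases pooled under Section 2.12:
- 90 µg: 30
- 135 µg: 30 + 180 = 210
- 180 µg: 30 + 180 = 210
- placebo: 30 + 90 = 120
- all VLA15: 450

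Section 6.1.3 states no test level; two-sided 5% is assumed. The SAP gives no AE rates, so all rates below are assumptions.

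**Method.** 5,000 simulated trials per scenario. The four-group Fisher-Freeman-Halton p-value comes from full enumeration of the 2×4 tables. The pooled test is Fisher's exact test of 450 versus 120. The planned sequence counts as a success if the overall test and at least one dose-versus-placebo test are significant. The simulation standard error is at most √(0.25/5000) = 0.7 points.

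| Placebo vs VLA15, same rate at all doses | Four-group test | Planned sequence | Pooled VLA15 vs placebo | Gain of pooled over four-group |
|---|---|---|---|---|
| 1% vs 4% | 24.2% | 23.2% | 30.4% | 6.2 |
| 1% vs 6% | 57.0% | 56.7% | 67.0% | 10.0 |
| 2% vs 8% | 59.3% | 59.2% | 70.1% | 10.8 |
| 5% vs 12% | 51.0% | 50.6% | 63.8% | 12.8 |
| 5% vs 15% | 79.4% | 79.3% | 89.0% | 9.6 |
| 10% vs 20% | 60.7% | 60.5% | 74.7% | 14.0 |

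Repeat runs agreed within about 2 points (for example 59% against 71% for 2% vs 8%, and 62% against 75% for 10% vs 20%).

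**Analytic cross-check**, 30% vs 45%. The noncentrality is λ = Σ nᵢ(pᵢ − p̄)² / [p̄(1 − p̄)], with p̄ = (450 × 0.45 + 120 × 0.30)/570 = 0.4184. The numerator is (450 × 120/570) × 0.15² = 2.132, so λ = 2.132/0.2433 = 8.76. Power is 70% on 3 df and 84% on 1 df.

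**Other patterns** (four-group against pooled):
- Mild gradient, 5% vs 10/12/14%: 63% against 73%. 10% vs 18/19/21%: 62% against 76%.
- Steep gradient, 5% vs 8/11/15%: 70.2% against 69.7%. 10% vs 13/16/20%: 51.0% against 52.9%.
- Effect at 180 µg only, 5% vs 12%: 68.3% against 17.7%. 10% vs 20%: 78.6% against 22.5%.
- Rare events, same rate at all doses, 1% vs 2%: 5% against 2%. 0% vs 2%: 9% against 7%. 1% vs 3%: 11% against 14%.
- No effect (rates of 2%, 5% and 10%): 4.3–5.0% against 2.7–3.9%.

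**Small strata**, rates 2 vs 8, 5 vs 12, 10 vs 20 and 20 vs 32%:
- Seropositive, assumed 10% of planned sizes (3/21/21/12): 4, 5, 6 and 9% against 0, 0.3, 3 and 7%.
- Ages 50–65 (about 60/60/30, with one nominal 90 µg subject): 8, 10, 17 and 18% against 3, 11, 20 and 21%.

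**The case against.** The strongest reply is that this is a choice and not a mistake. The primary objective is to find the optimal dose, the sample size is argued from exposure per dose, and the SAP sets no AE hypothesis, power or alpha. A dose-resolved test suits that aim, and the pooled column with its interval already lets a reader see the contrast. This stands in part. The plan does not contradict itself here, and the four-group test is the better one when doses differ. But the plan does test AE rows and does pool the vaccine groups for display, and intervals for single rates are not an interval for a difference.

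Three stronger readings are tempting, and the documents do not support them.
- A reader might infer that the four-group test is the only one planned. Section 6.1.3 also provides pair-wise tests, which include each dose against placebo. They are gated on the overall result, so they cannot rescue an effect that it misses.
- A reader might expect the loss to be greatest in the stratified Tables 14.1.4.2 to 14.1.4.4. At the rates checked, both tests have little power there and the pooled test gains little or nothing.
- A reader might expect rare SAEs or AESIs to be picked up. At VLA15 rates of 1 to 3% neither test is useful.

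It is also fair to object that an extra test on every SOC and PT row would multiply unadjusted p-values. That is why the change below is kept to summary and overall rows.

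**Conclusion.** The gap is real but limited. No test or difference interval compares pooled VLA15 with placebo. For AEs with a VLA15 rate of roughly 4% or more and similar rates across doses, this costs about 6 to 14 points of power in the full sample, and the gated pair-wise tests leave that loss in place. The size rests on planned group sizes, a two-sided 5% level and assumed AE rates. It remains under a mild dose gradient, vanishes under a steep one, and turns into a large loss if only 180 µg carries the effect. The pooled contrast therefore belongs beside the existing tests and cannot replace them. The change is worth making because it is cheap and sharpens the safety comparison; it alters no primary result.

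**What to change.** In Section 6.1.3, pre-specify one comparison of pooled 135 and 180 µg VLA15 with placebo, not conditional on the four-group test, with a 95% CI for the difference in rates. Give all three doses pooled versus placebo as support. Keep the four-group and pair-wise tests.

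Stratify the comparison by study phase, for example with an exact stratified test and a Mantel-Haenszel risk difference. The ratio of 135 + 180 µg to placebo is 60:30 in the Run-in and 360:90 in the Main phase. Run-in subjects are thus 30/120 = 25% of placebo but 60/420 = 14.3% of the pooled doses. If the AE rate differs between phases by d, a crude difference is shifted by (0.143 − 0.25) × d = −0.107d. Phases differ in age range, and the Run-in has two extra safety contacts after the first vaccination, so d need not be zero.

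Apply it to the summary rows of Table 14.1.4.1 and to the overall rows of the medically attended (14.1.4.8, 14.1.4.9) and the unsolicited, related and severe AE tables (14.1.4.48 to 14.1.4.51). Mark these tables in Section 7.1.4, and label the p-values nominal and unadjusted.

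Cost: SAP wording, a few table cells and some additional nominal p-values, with no new data. Leaving out the 90 µg group loses little: unstratified power for 420 versus 120 is 69%, 63% and 73% at 2 vs 8, 5 vs 12 and 10 vs 20%. Power of the stratified version was not computed. The change should be fixed before the unblinding for the Day 85 interim analysis.

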7.2 List of Data Listings

7.2.1 Overall Study Information

[figure not shown]
No	Legend	Content
Listing 16.2.1.1.1:	Subject overview	Subject ID, Country, Site Name, Study Part, Date of signed informed consent, Subject eligible to be randomized, Reason not randomized, Planned Treatment, Actual Treatment, Safety/mITT Population, Reason not in Safety/mITT Population, PP Population, Reason not in PP Population
Listing 16.2.1.1.2:	Screening Failure with Reason	Subject ID, Withdrawal of consent, In/Ex criteria not met, Other reason screening failure, Specification of other reason for screening failure
Listing 16.2.1.1.3:	In/Exclusion Criteria that were not Met	Subject ID, Visit, Criterion ID not met, Criterion description
Listing 16.2.1.1.4:	Study Vaccination (Vaccinated Subjects)	Subject ID, Group, Visit, Vaccination administered, Reason if not Administered, Date, Time, Kit number, Location, Other location (specification/reason)
Listing 16.2.1.1.5:	Visit Log (Vaccinated Subjects)	Subject ID, Group, Visit, Visit performed, Visit Date, Reason visit not performed, Deviation from time window [days], Reason outside time window, Age, Reason for unscheduled visit, Type of contact (ET visit)
Listing 16.2.1.1.6:	Missed Visits, Missed Vaccinations, Early Terminations: Part I (Vaccinated Subjects)	Subject ID, Group, Visit attendance, All vaccinations administered, Primary reason treatment discontinuation, Other reason for treatment discontinuation, AE Term (treatment discontinuation), Reason for recommended withdrawal (treatment discontinuation), Individual stopping criteria, AE Term (stopping criteria)
Listing 16.2.1.1.7:	Missed Visits, Missed Vaccinations, Early Terminations: Part II (Vaccinated Subjects)	Subject ID, Group, Is the primary reason for treatment discontinuation the same as for early termination, Primary reason for early termination, Other reason for early termination, AE Term (early termination), Reason for recommended withdrawal (early termination), Death date, Primary cause of death, Date of ET, Last attended scheduled visit before ET

Listing 16.2.1.1.8:	Protocol Deviations (Vaccinated Subjects)	Subject ID, Group, PD Category, PD Description, Severity, Reason for classification
Listing 16.2.1.1.9:	Visits Performed as Phone Call Due to Covid-19 (Vaccinated Subjects)	Subject ID, Group, Visit, Visit performed, Visit Date, Reason visit not performed, Deviation from time window [days], Reason outside time window, Age, Reason for unscheduled visit, Type of contact (ET visit) Only applicable for IA D236

7.2.2 Baseline

No	Legend	Content
Listing 16.2.1.2.1:	Demographics (Vaccinated Subjects)	Subject ID, Group, Gender, Childbearing potential, Reason no childbearing potential (other), Year of birth, Age at Screening [years], Age group, Race (other), Body height [cm], Body weight [kg], BMI [kg/m2]
Listing 16.2.1.2.2:	Physical Examination at Screening (Vaccinated Subjects)	Subject ID, Group, Visit, Physical examination performed, Reason not performed, Examination Date
Listing 16.2.1.2.3:	ECG (Vaccinated Subjects)	Subject ID, Group, ECG performed, Date, Reason ECG not performed, ECG Result, ECG clinically relevant
Listing 16.2.1.2.4:	HIV Test (Vaccinated Subjects)	Subject ID, Group, Test performed, Reason test not performed, Date, Result
Listing 16.2.1.2.5:	Medical History (Vaccinated Subjects)	Subject ID, Group, Condition, MedDRA PT (MedDRA 22.1), MedDRA SOC (MedDRA 22.1), Start Date, End Date, Ongoing at study entry
Listing 16.2.1.2.6:	Prior Medications (Vaccinated Subjects)	Subject ID, Group, Medication or therapy, Start Date, End Date, ATC term level 2 (WHODRUG GLOBAL B3 September 1 2019), ATC term level 3 (WHODRUG GLOBAL B3 September 1 2019), Dose Unit, Dose Form, Frequency, Route, Indication category, Indication
Listing 16.2.1.2.7:	Concomitant Medications (Vaccinated Subjects)	Subject ID, Group, Medication or therapy, Start Date, End Date, ATC term level 2 (WHODRUG GLOBAL B3 September 1 2019), ATC term level 3 (WHODRUG GLOBAL B3 September 1 2019), Dose Unit, Dose Form, Frequency, Route, Indication category, Indication
Listing 16.2.1.2.8:	Prior Procedures (Vaccinated Subjects)	Subject ID, Group, Procedure, Start Date, CP ongoing at study end, End Date, Indication category, Indication, MedDRA PT (MedDRA 22.1 English), MedDRA SOC (MedDRA 22.1 English)
Listing 16.2.1.2.9:	Concomitant Procedures (Vaccinated Subjects)	Subject ID, Group, Procedure, Start Date, CP ongoing at study end, End Date, Indication category, Indication, MedDRA PT (MedDRA 22.1 English), MedDRA SOC (MedDRA 22.1 English)
Listing 16.2.1.2.10:	Vaccination History (Vaccinated Subjects)	Subject ID, Group, Date of Vaccination, Vaccination (indication or trade name), ATC term level 3 (WHODRUG GLOBAL B3 September 1 2019)

7.2.3 Immunogenicity

No	Legend	Content
Listing 16.1.3.1:	ELISA: Immunogenicity Results Part 1 (Treated Subjects)	Subject number, Planned Treatment (mITT), Sample excluded from PP analysis, Visit, Date of visit, Time of visit, Sample drawn, Reason for not drawn, Sample ID, Worklist ID, Antigen, IgG titer [U/mL] (measured), Sample Status, IgG titer [U/mL] (analysis), Fold increase from Day 0, ELISA Seroconversion since V1
Listing 16.1.3.2:	ELISA: Immunogenicity Results Part 2 (Treated Subjects)	Subject number, Planned Treatment (mITT), Sample excluded from PP analysis, Visit, Date of visit, Time of visit, Seroconversion for all six serotypes ST1-6, Seroconversion for ST1 and ST2

7.2.4 Safety

No	Legend	Content
Listing 16.2.1.4.1.1:	Unsolicited Adverse Events Part I (Vaccinated Subjects)	Patient ID, Group, Adverse Event, MedDRA PT (MedDRA 22.1), MedDRA SOC(MedDRA 22.1), Start date, Start time, Study day of onset, Onset after vacc., Onset (relative to previous vacc.) [days], End Date, End time, Duration of AE [days]
Listing 16.2.1.4.1.2:	Unsolicited Adverse Events Part II (Vaccinated Subjects)	Patient ID, Group, Adverse Event, Event considered as AESI, Specialist work-up performed, Medically attended, Serious adverse event, SAE criteria, Severity, Causality, Action taken on IMP, Action taken general, Outcome
Listing 16.2.1.4.1.3:	Related Unsolicited Adverse Events Part I (Vaccinated Subjects)	See Listing 16.2.1.4.1.1
Listing 16.2.1.4.1.4:	Related Unsolicited Adverse Events Part II (Vaccinated Subjects)	See Listing 16.2.1.4.1.2
Listing 16.2.1.4.1.5:	Severe Unsolicited Adverse Events Part I (Vaccinated Subjects)	See Listing 16.2.1.4.1.1
Listing 16.2.1.4.1.6:	Severe Unsolicited Adverse Events Part II (Vaccinated Subjects)	See Listing 16.2.1.4.1.2
Listing 16.2.1.4.1.7:	Serious Adverse Events Part I (Vaccinated Subjects)	See Listing 16.2.1.4.1.1
Listing 16.2.1.4.1.8:	Serious Adverse Events Part II (Vaccinated Subjects)	Patient ID, Group, Adverse Event, Type of AE, Event considered as AESI, Specialist work-up performed, Medically attended, Serious, SAE criteria, Severity, Causality, Action taken on IMP, Action taken general, Outcome
Listing 16.2.1.4.1.9:	Medically Attended Adverse Events Part I (Vaccinated Subjects)	See Listing 16.2.1.4.1.1
Listing 16.2.1.4.1.10:	Medically Attended Adverse Events Part II (Vaccinated Subjects)	See Listing 16.2.1.4.1.8

Adapted from:

STAT03_A Statistical Analysis Plan

Version 6.0, Effective Date 16-Feb-2018

Confidential and intellectual property of [REDACTED]. No part of this document or its contents may be duplicated, referenced, published or otherwise disclosed in any form or by any means without prior written consent of [REDACTED]

Listing 16.2.1.4.1.11:	Adverse Events Resulting in Death Part I (Vaccinated Subjects)	See Listing 16.2.1.4.1.1
Listing 16.2.1.4.1.12:	Adverse Events Resulting in Death Part II (Vaccinated Subjects)	See Listing 16.2.1.4.1.8
Listing 16.2.1.4.1.13:	Adverse Events Leading to Withdrawal from Further Vaccination (Vaccinated Subjects)	Patient ID, Group, Adverse event term, MedDRA PT (MedDRA 22.1), MedDRA SOC(MedDRA 22.1), Severity, Causality, Start date, Withdrawn from further vacc. after vacc., Onset (relative to previous vacc.) [days], Estimated Duration of AE (incl. missing stop date) [days]
Listing 16.2.1.4.1.14:	Adverse Events Leading to Withdrawal from the Study (Vaccinated Subjects)	Patient ID, Group, Adverse event term, MedDRA PT (MedDRA 22.1), MedDRA SOC(MedDRA 22.1), Severity, Causality, Start date, Withdrawn from study after vacc., Onset (relative to previous vacc.) [days], Estimated Duration of AE (incl. missing stop date) [days]
Listing 16.2.1.4.1.15:	Adverse Events with Missing Assessment (eCRF Section "AE log") Part I (Vaccinated Subjects)	See Listing 16.2.1.4.1.1
Listing 16.2.1.4.1.16:	Adverse Events with Missing Assessment (eCRF Section "AE log") Part II (Vaccinated Subjects)	See Listing 16.2.1.4.1.8
Listing 16.2.1.4.1.17:	Solicited Adverse Events by Diary Day (Vaccinated Subjects)	Patient ID, Group, Symptom, Present after vaccination, Serious, Medically attended, Taken any medication due to symptom, Withdrawn from further vaccination, Withdrawn from study, Time point, Symptom ongoing after Day 6, Meets FDA Toxicity Grading Scale, Grade per diary day (incl. not present), Size [cm], Oral body temperature [°C]
Listing 16.2.1.4.1.18:	Severe Solicited Adverse Events by Diary Day (Vaccinated Subjects)	See Listing 16.2.1.4.1.17
Listing 16.2.1.4.1.19:	Solicited Adverse Events with Missing Assessments by Diary Day (Vaccinated Subjects)	See Listing 16.2.1.4.1.17
Listing 16.2.1.4.1.20:	Solicited Adverse Events by Diary Period (Vaccinated Subjects)	Patient ID, Group, Symptom, Present after vaccination, Serious, Medically attended, Taken any medication due to symptom, Withdrawn from further vaccination, Withdrawn from study, Onset (relative to previous vacc.) [days], Stop day (relative to previous vacc.) [days], Maximum severity (grade 0-4 and n/p)
Listing 16.2.1.4.1.21:	Severe Solicited Adverse Events by Diary Period (Vaccinated Subjects)	See Listing 16.2.1.4.1.21
Listing 16.2.1.4.2.1:	Hematology Values Outside Normal Range or Meeting FDA Grading Scale for Lab Assessments	Patient ID, Group, Visit, Date, Time, Parameter, FDA Grading, Result, Unit, Lower Limit, Upper Limit, Result (converted), Unit (converted), Lower limit (converted), Upper limit (converted), Out of normal

	(Vaccinated Subjects)	range, Clinically relevant, Likely cause (if available)
Listing 16.2.1.4.2.2:	Clinical Chemistry Values Outside Normal Range or Meeting FDA Grading Scale for Lab Assessments (Vaccinated Subjects)	See Listing 16.2.1.4.2.1
Listing 16.2.1.4.2.3:	Coagulation Values Outside Normal Range (Vaccinated Subjects)	Patient ID, Group, Visit, Date, Parameter, Result, Unit, Lower Limit, Upper Limit, Result (converted), Unit (converted), Lower limit (converted), Upper limit (converted), Out of normal range, Clinically relevant, Likely cause (if available)
Listing 16.2.1.4.2.4:	Urinalysis Values Outside Normal Range (Vaccinated Subjects)	Patient ID, Group, Visit, Date, Time, Test, Result, Clinically relevant, Likely cause (if available)
Listing 16.2.1.4.3.1:	Vital Signs by Visit (Vaccinated Subjects)	Patient ID, Group, Visit, Specifier, Date, Time, Systolic Blood Pressure [mmHg], Diastolic Blood Pressure [mmHg], Pulse Rate [beats/min], Oral body temperature [°C]
Listing 16.2.1.4.3.2:	Physical Examination (Vaccinated Subjects)	Patient ID, Group, Visit, Specifier, Examination Date, Examination Time, Type of physical examination, Physical examination performed, Reason physical examination/observation not performed
Listing 16.2.1.4.3.3:	Pregnancy Test (Vaccinated Female Subjects)	Patient ID, Group, Visit, Date, Time, Pregnancy test performed, Reason not performed, Type, Result
Listing 16.2.1.4.3.4:	Injection Site Inspection (Vaccinated Subjects)	Patient ID, Group, Visit, Date, Time, Inspection of injection site performed, Reason not performed, Any findings
Listing 16.2.1.4.3.5:	Body Temperature in Case of Fever (Vaccinated Subjects)	Patient ID, Group, Visit, Time point, Body temperature [°C]
Listing 16.2.1.4.3.6:	Lyme Borreliosis Screening (Vaccinated Subjects)	Patient ID, Group, Visit, Date, Sample analysis performed, Reason not collected/Performed, Result (C6 ELISA assay), Confirmatory immunoblot performed, Reason conf. immunoblot not done, IgM Result (Immunoblot), IgG Result (Immunoblot), B.b. s.l. serostatus
Listing 16.2.1.4.3.7:	Vaccination Delay Criteria (Vaccinated Subjects)	Patient ID, Group, Visit, Checklist question, Answer

